### **3.9.2. Suicidality**

The proportion of participants who report any post-baseline suicidal ideation or any post-baseline suicidal behavior will be summarized by treatment group. Suicidal behaviors will include: actual attempts, non-suicidal self-injurious behavior, interrupted attempts, aborted attempts, preparatory acts or behaviors, and completed suicide. The most severe ideation, maximal frequency, maximal duration, minimal controllability, minimal deterrents, maximal reasons for ideation, maximal actual lethality or medical damage, and maximal potential lethality will be summarized as means, standard deviations, medians, and ranges by treatment group.

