4.3 Criteria for Withdrawal from Study Drug or Study Participation

4.3.1 Study Drug Withdrawal

Investigators must contact the Medical Monitor to discuss any of the following events which may lead to the patient discontinuing study drug:

1. Patient is noncompliant with the study procedures or medications.
2. Patient takes prohibited concomitant medications as defined in this protocol or receives prohibited neurosurgical intervention for PD.
3. Patient has a clinically significant out-of-range laboratory value(s) or clinically significant abnormal finding(s) on physical examination or intolerable AEs (as determined by the patient) or that put the patient at additional risk as judged by the Investigator.
4. Patient's PDD symptoms worsen to the extent that, in the judgment of the Investigator, they require the addition of new anti-dementia medication or an increase in the dose of their concomitant cholinesterase inhibitor medication.

Any withdrawal of a patient from the study or discontinuation of study drug should be discussed with the Medical Monitor. Patients must discontinue study drug if any of the following events occur:

1. Patient develops an illness that would interfere with his or her continued participation.
2. Patient or caregiver (or legal representative, if applicable) withdraws consent.
3. There is confirmation of a pregnancy during the study, as evidenced by a positive pregnancy test.
4. The Sponsor/Sponsor's designee or a regulatory agency requests withdrawal of the patient.
5. The Sponsor or a regulatory agency terminates the study.

6. Patient has active suicidality since last visit as indicated by a positive response (“Yes”) to either Question 4 or Question 5 of the C-SSRS, or reports any suicidal behavior since their last C-SSRS assessment. The patient should be referred immediately to a Mental Healthcare Professional.
7. The patient has a QTcF interval consistently \geq 500 msec and/or a QTcF interval consistently increased by \geq 60 msec compared to the average baseline QTcF interval (see **Section 7.16**). The average baseline QTcF interval is defined as the average of the three QTcF interval values obtained at Visit 2. Fridericia’s method must be used for correction of QT intervals.
8. Investigators must follow guidelines provided related to monitoring hepatic parameters in relation to investigation guidelines and stopping rules. The following necessitate immediate cessation of dosing with IMP:

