10.8 Determination of Sample Size

A total sample size of 80 or 40 in each group will provide at least 80% power to detect a true treatment difference equal to an effect size of 0.69 assuming up to 15% loss to follow up and using a two-tailed test at alpha = 0.05 based on a simple two-sample t-test. Additional power will be obtained from the proposed analysis using a shared-baseline repeated measures ANOVA.

Approximately 120 patients will be screened, assuming a 33% screen failure rate, to randomize 80 patients.

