### 3.2.2. Safety Endpoints

The following safety endpoints will be evaluated:

- Proportion of participants experiencing the following and event rates relative to time at risk of: (a) any treatment-emergent AE (TEAE), (b) any severe TEAE, (c) any serious TEAE, (d) any TEAE at least possibly related to study drug, (e) any TEAE leading to permanent study drug discontinuation or early termination from the trial, and (f) any TEAE resulting in death, summarized across all MedDRA terms
- Proportion of participants experiencing and number of unique events of all TEAEs classified by seriousness, severity, relatedness to study drug, action taken with study drug, and outcome, summarized across all MedDRA terms
- Proportion of participants experiencing and number of unique events of each type of TEAE and serious TEAE classified by MedDRA system organ class, high level term, and preferred term
- Proportion of participants experiencing treatment-emergent orthostatic hypotension
- Mean 16-week change from baseline in supine and standing SBP, supine and standing DBP, and differences from supine to standing SBP and DBP
- Mean 16-week change from baseline in weight
- Proportion of participants experiencing treatment-emergent clinically significant laboratory abnormalities classified by assay, whether the abnormality is below or above the normal range, and visit, with cross-classification of frequencies of abnormalities from baseline to each scheduled post-baseline visit at which safety labs are performed
- Mean 16-week change from baseline in laboratory assays
- Proportion of participants experiencing treatment-emergent clinically significant ECG abnormalities
- Mean 16-week change from baseline in ECG parameters
- Mean 16-week change from baseline in UPDRS Part I score, II score, III score, I through III total score, Part IV dyskinesia score, Part IV clinical fluctuations score, Part IV other complications score, and Part IV total score
- Mean 16-week change from baseline in levodopa daily dosage (LDD) and levodopa equivalent daily dosage (LEDD)
- Proportion of participants reporting any treatment-emergent suicidal ideation
- Maximum post-baseline suicidal ideation planning, frequency, duration, controllability, deterrents, and reasons

- Proportion of participants reporting any post-baseline suicidal behavior, actual attempts, non-suicidal self-injurious behavior, interrupted attempts, aborted attempts, preparatory acts or behaviors, or completed suicide

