- Maximum post-baseline suicidal behavior lethality and potential lethality

Reported proportions will use as their denominator all participants in the Safety and Tolerability sample (see [Section 3.5](#) below).

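### SAP 3.9.2 lists non-suicidal self-injury among the suicidal behaviours, so the overall suicidal-behaviour proportion could be overstated

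*SAP*

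**What the plan says.** SAP 3.9.2 (Suicidality) sets the summary: "The proportion of participants who report any post-baseline suicidal ideation or any post-baseline suicidal behavior will be summarized by treatment group". It then defines the second term: "Suicidal behaviors will include: actual attempts, non-suicidal self-injurious behavior, interrupted attempts", and the list goes on to aborted attempts, preparatory acts and completed suicide, six items in all.

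SAP 3.2.2 (Safety Endpoints) covers the same ground in a single bullet: "Proportion of participants reporting any post-baseline suicidal behavior, actual attempts, non-suicidal self-injurious behavior, interrupted attempts, aborted attempts, preparatory acts or behaviors, or completed suicide". The section closes with the denominator rule: "Reported proportions will use as their denominator all participants in the Safety and Tolerability sample".

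The planned size is in Protocol 10.8: "A total sample size of 80 or 40 in each group".

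The introduction to the SAP makes the SAP authoritative over the protocol on matters of analysis, so the wording of 3.9.2 is what a programmer would follow.

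**The concern.** A composite should contain only events that its label describes. Here one of six components is, by its own name, not suicidal. A participant with that event and no other would be reported under a heading that the SAP's own terminology says does not apply.

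Suicidality is a named safety objective, assessed with the C-SSRS, and the trial is small. If other suicidal behaviours are rare or absent, a single participant classified in this way could account for the whole proportion shown for an arm. Someone reading only the overall row would have no reason to suspect it.

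**Working it through.** The documents state no expected figure for this proportion, so there is none to reproduce. The check is a comparison of texts followed by simple arithmetic.

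**Step 1: is the item in or out of the overall count?**

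| Place | What it does with non-suicidal self-injury |
|---|---|
| SAP 3.9.2 | Names it as one of the suicidal behaviours, directly after the sentence that promises the overall proportion |
| SAP 3.2.2 | Puts it in one *or* list with the overall category; can be read as one proportion per item, but says nothing about keeping it out of the overall one |
| Protocol 7.10 | Names four broad C-SSRS categories and places non-suicidal self-injury in none of them |
| Protocol 4.2 (exclusion 10) and 4.3.1 | Use the term suicidal behaviour without listing its components |

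Only 3.9.2 gives a definition, and it puts the item in. Nothing elsewhere takes it out or gives a reason for including it.

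**Step 2: effect on the reported proportion.**

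Inputs: n = 40 per arm (Protocol 10.8, planned); k = number of participants in the arm with non-suicidal self-injury and no other listed behaviour (not given in the documents).

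Overstatement in that arm = k/n:

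- k = 0: 0/40 = 0 points
- k = 1: 1/40 = 2.5 points
- k = 2: 2/40 = 5.0 points
- k = 3: 3/40 = 7.5 points

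The actual n is the number in the Safety and Tolerability sample by treatment received. If that were, say, 38 in an arm, one participant would count for 1/38 = 2.6 points.

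**Step 3: effect on the comparison of arms.**

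The error can widen or narrow the visible difference. Suppose no participant has any other listed behaviour and one on SYN120 has non-suicidal self-injury only. The table then shows 1/40 against 0/40, a difference of 2.5 points where the correctly labelled difference is 0. Suppose instead that one participant on SYN120 has a true suicidal behaviour and one on placebo has non-suicidal self-injury only. The table then shows 1/40 against 1/40, a difference of 0 where the correctly labelled difference is 2.5 points.

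**Step 4: how likely is k of at least 1 across the trial?**

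The rate p of such participants is an assumption. P(at least one among 80) = 1 − (1 − p)^80:

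| Assumed p | P(at least one in 80) |
|---|---|
| 0.5% | 33% |
| 1% | 55% |
| 2% | 80% |
| 5% | 98% |

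The range shows only that the answer depends on a rate that the documents do not supply.

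**The case against.** The best defence is SAP 3.2.2. Its natural reading is one proportion per item, with non-suicidal self-injury beside the overall category and not inside it. On that reading, the itemised table would show what the event was, and the list in 3.9.2 may be no more than a loosely worded inventory of the items to tabulate. Part of this stands: a careful reader of an itemised table could recover the truth, and a separate line may already be intended. But 3.2.2 does not define the overall category and 3.9.2 does, so the overall row would still be mislabelled if programmed as written.

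A second defence is that little depends on it. SAP 3.9.2 names no test, threshold or decision rule, and Protocol 10.5.1 promises only a description of suicidal ideation. Exclusion criterion 10 also keeps out patients with suicidal behaviour or the two most severe ideation types in the past 6 months. Within an arm, the error can only add to a harm count and cannot hide an event. All of this stands and keeps the point minor. It does not make the label right, and Step 3 shows that the contrast between arms can be blurred in either direction.

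A reader might also infer that the table would disagree with the category that the protocol uses for eligibility and for stopping study drug, where 4.3.1 refers to a patient who "or reports any suicidal behavior since their last C-SSRS assessment". The documents do not support that. Neither protocol section lists what the term covers, so no mismatch can be shown. In any case a table definition does not alter who is enrolled or withdrawn.

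**Conclusion.** The definition in SAP 3.9.2 contradicts its own label, and 3.2.2 does not clearly repair it. The consequence is conditional. Each participant with non-suicidal self-injury and no other listed behaviour overstates the arm's overall suicidal-behaviour proportion by about 2.5 percentage points at the planned 40 per arm. It would be tempting to say that the reported proportion is wrong outright. That goes too far: without such a participant the number is the same under either definition, and the documents give no rate for these events.

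The conclusion rests on two assumptions: that the overall row is built as 3.9.2 states, and that the arms are close to their planned size. The summary is descriptive, so efficacy, alpha and power are untouched. This is a small correction worth making, not a threat to the trial's conclusions.

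**What to change.** Before unblinding, remove non-suicidal self-injury from the list of suicidal behaviours in SAP 3.9.2 and report it on its own line. Reword the bullet in 3.2.2 so that it states which items make up the overall proportion and shows non-suicidal self-injury as a separate proportion. If the broader composite is wanted, keep it but relabel it, for example as *suicidal or self-injurious behavior*, in both sections.

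Either choice loses no data, needs no new collection and changes one table definition. Settling it while blinded means that the classification cannot be influenced by the arm in which an event falls.

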### **3.9.3. Safety Labs**

The absolute level and the absolute change from baseline for each safety laboratory assay will be summarized as means, standard deviations, medians, and ranges at each visit by treatment group. The proportion of participants with safety lab levels below the lower limit of normal or above the upper limit of normal will be summarized by treatment group by visit and at any post-baseline visit. Shift tables will be used to summarize changes in laboratory assays from baseline to the week 4, 8, and 16 visits when classified as below the lower limit of normal, within normal limits, and above the upper limit of normal separately by treatment group.

### **3.9.4. Vital Signs**

The absolute level and the absolute change from baseline for vital signs will be summarized as means, standard deviations, medians, and ranges at each visit by treatment group.

### **3.9.5. Blood Pressure**

The absolute level and the absolute change from baseline of supine and standing SBP, supine and standing DBP, and differences from supine to standing SBP and DBP will be summarized as means, standard deviations, medians, and ranges at each visit by treatment group. The proportion of participants who experience orthostatic hypotension (as defined in [Section 3.3.11](#)) at the week 4, 8, and 16 visits and at any post-baseline visit will be summarized by treatment group.

### **3.9.6. Additional Continuous Safety Outcomes**

The additional continuous safety outcomes of weight, ECG parameters, UPDRS scores (Part I score, Part II score, Part III score, Parts I through III total score, Part IV dyskinesia score, Part IV clinical fluctuations score, Part IV other complications score, and Part IV total score), LDD, and LEDD and their absolute change from baseline will be summarized as means, standard

deviations, medians, and ranges at each visit by treatment group. Treatment-dependent differences in 16-week change scores will be estimated in the ST sample for UPDRS scores using the shared-baseline, repeated-measures analysis of variance described for the primary efficacy analysis in [Section 3.8.1](#).

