4.3.2 Withdrawal from Study Participation

Patients are free to withdraw from the study at any time, without prejudice to their continued care.

All patients who discontinue prematurely from the study will be requested to return for a clinic visit that includes all safety procedures and efficacy measures as outlined for the Early Termination Visit in the Schedule of Events/Evaluations (**Table 1**). The Early Termination Visit should be done under IMP treatment, if possible.

For any early discontinuation, the patient will be requested to return for a Safety Follow-Up Visit 14 days after the last dose of IMP, unless the Early Termination Visit itself occurs 14 or more days after the last dose of IMP. All treatment-emergent, clinically significant AEs will be followed until resolution, return to Baseline level, or stabilization.

Patients who prematurely withdraw from the study will not be replaced.

Investigators should attempt to obtain information on patients in the case of study withdrawal. Participants who discontinue study drug but do not withdraw consent should continue to be followed according to the normal schedule of assessments. For patients considered lost to follow up, the Investigator should make an effort (at least one phone call and one written message to the patient) and document his or her effort (include the date and summary of the phone call(s) and a copy of the written message(s) in the source documents) to complete the final evaluation. All results of these evaluations and observations, together with a narrative description of the reason(s) for removing the patient, must be recorded in the source documents. The electronic case report form (eCRF) must document the primary reason for study withdrawal or discontinuation.

Investigators should contact the Medical Monitor, whenever possible, to discuss in advance the withdrawal of a patient from the study.

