6.2.5 Visit 4 (Week 4) Study Visit

Note: Confirm the arrangement for laboratory sample pick-up on the day of the Week 4 visit with the courier (see Central Laboratory Procedures Manual).

1. Assess AEs by asking open-ended queries and record the assessments.
2. Record concomitant medication use; assess and record any changes to anti-dementia or anti-Parkinson medication doses or regimens.
3. Obtain and record BP and pulse after at least 5 minutes supine rest and again after standing for approximately 1 and 3 minutes.
4. Perform physical and neurological exam.

5. Perform full UPDRS Parts I, II III (motor) and IV.

For patients with motor fluctuations: Perform full UPDRS Parts I, II III (motor) and IV, approximately 1 to 3 hours after the patient has taken a scheduled dose of levodopa (preferably their morning dose of levodopa). UPDRS in ON will be measured at a time representative of the ON state in that patient, not in “best” ON.

6. Administer C-SSRS.

7. Obtain 12-lead ECG and ensure the ECG is collected at a time when the patient is not experiencing dyskinesia that would interfere with an adequate recording.

8. Obtain samples for the following laboratory tests and record the date and time of collection:

a. Females of childbearing potential: Obtain urine hCG pregnancy test; verify method of contraception has not changed since Screening.

b. Hematology and chemistry (including liver function tests).

c. Blood sample for SYN120 plasma concentration [REDACTED]
[REDACTED] Obtain and record the date and time when the patient took the last dose of IMP. Record the date and time of SYN120 sample collection.

d. Blood sample for optional pharmacogenetic substudy (only if patient gave consent for the pharmacogenetic substudy and specimen was NOT collected during a previous visit): A single blood sample (approximately 10 mL) will be collected per patient. See **Section 7.13.**

e. Urine sample for urinalysis.

Note: For processing, labeling and shipping of samples, follow the instructions provided in the Central Laboratory Procedures Manual.

9. Obtain the returned blister cards dispensed at the Baseline Visit:

a. Assess and document the IMP accountability and compliance (document any missed dose(s), lost tablets and number of tablets taken).

b. Review and reconcile any discrepancies with the patient and caregiver.

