## 3.8. Efficacy Analysis

### 3.8.1. Primary Analysis of the Primary Efficacy Endpoint

The primary efficacy analysis will be performed on the mITT sample using the adjudicated CDR data and will use a shared-baseline, repeated-measures analysis of variance that includes fixed effects for visit (3 levels: Baseline, Week 8, and Week 16) and the interaction between treatment group (2 levels: SYN120 and placebo) and post-baseline visit (2 levels: Weeks 8 and 16), random center-specific intercepts, and unstructured within-person covariance. The interaction between treatment group and visit will be restricted to post-baseline visits by including a numeric indicator variable (0 pre-treatment, 1 post-treatment) in the interaction. Use of a shared baseline reflects the true state of the population sampled prior to randomization and has the advantage of adjusting for any chance differences at baseline in a manner similar to analysis of covariance ([Liang and Zeger, 2000](#)) with potentially greater efficiency with more than one follow-up visit and drop-out. Data from Early Termination visits will be assigned to the next scheduled post-baseline visit. The following SAS code specifies the model:

```
proc mixed data=xxx method=reml;
  class site id trtrnd visit;
  model Value = visit post*trtrnd*visit;
  random intercept / subject=site type=vc;
  repeated visit / subject=id(site) type=un;
```

Treatment-dependent differences in the change from baseline to the week 16 visit on the CDR COA will be estimated by a linear contrast and tested using a two-tailed Wald-test at alpha = 0.05. The following SAS code specifies the linear contrasts used to estimate treatment- and visit-specific means, treatment- and visit-specific changes from baseline, and treatment-dependent visit-specific changes from baseline (with the sort order for treatment group being SYN120 first and placebo second):

```
estimate "0|Active |Wk  00" intercept 1 visit  1 0 0 post*trtrnd*visit 0 0 0  0 0 0 / cl;
estimate "0|Active |Wk  08" intercept 1 visit  0 1 0 post*trtrnd*visit 0 1 0  0 0 0 / cl;
estimate "0|Active |Wk  16" intercept 1 visit  0 0 1 post*trtrnd*visit 0 0 1  0 0 0 / cl;
estimate "1|Active |dWk 08" intercept 0 visit -1 1 0 post*trtrnd*visit 0 1 0  0 0 0 / cl;
estimate "1|Active |dWk 16" intercept 0 visit -1 0 1 post*trtrnd*visit 0 0 1  0 0 0 / cl;
estimate "0|Placebo|Wk  00" intercept 1 visit  1 0 0 post*trtrnd*visit 0 0 0  0 0 0 / cl;

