### 3.8.3. Secondary Efficacy Endpoints

The key secondary efficacy endpoint will all be analyzed using the same analysis samples and models as specified for the primary efficacy endpoint in [Sections 3.8.1](#) and [3.8.2](#). Non-key secondary efficacy endpoints and exploratory efficacy endpoints will all be analyzed using the mITT sample and the primary efficacy analysis described in [Section 3.8.1](#). Variables that are strictly positive and strongly right-skewed (e.g., CDR POA, CDR SWM, and other CDR measures of reaction time) will be analyzed on their original scale and after log-transformation. Estimates from analysis of log-transformed data will be back-transformed for reporting.

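### Read literally, the UPDRS between-arm model in SAP 3.9.6 has no Week 4 level, so its Week 16 estimate can be biased if withdrawal depends on Week 4 motor scores

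*SAP*

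**What the plan says.** For the between-arm UPDRS comparison, SAP 3.9.6 says: "Treatment-dependent differences in 16-week change scores will be estimated in the ST sample for UPDRS scores using the shared-baseline, repeated-measures analysis of variance". It then points to SAP 3.8.1 for the description of the model.

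The model in 3.8.1 has "fixed effects for visit (3 levels: Baseline, Week 8, and Week 16") and treatment interacting with "post-baseline visit (2 levels: Weeks 8 and 16"). The printed ESTIMATE statements carry coefficients for three visits per arm. This is the CDR schedule; the CDR is not given at Week 4.

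UPDRS has a different schedule. At Visit 4 (Week 4) Protocol 6.2.5 instructs: "Perform full UPDRS Parts I, II III (motor) and IV". It is rated again at Weeks 8 and 16 and at Early Termination.

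Three other provisions bear on the point:
- SAP 3.9.6 also summarizes UPDRS scores and their changes as means, standard "deviations, medians, and ranges at each visit by treatment group".
- SAP 3.8.1 says: "Data from Early Termination visits will be assigned to the next scheduled post-baseline visit".
- Protocol 4.3.2 says: "Participants who discontinue study drug but do not withdraw consent should continue to be followed according to the normal schedule of assessments".

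**The concern.** Protocol 10.4.1 and SAP 3.8.6 justify the repeated-measures model on the ground that it is unbiased when missing data can be predicted from observed scores. That protection covers only scores that are in the model. A patient with Baseline and Week 4 UPDRS who leaves before Week 8 without an Early Termination exam contributes only a baseline value to a three-visit fit. If the Week 4 score influenced the decision to leave, the fit has discarded the variable that would have made the missingness ignorable.

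Such a link is plausible. The titration reaches 100 mg after 14 days, so Week 4 is the first UPDRS at full dose. The protocol synopsis also lists worsening motor function that needs new medication as a reason to stop study drug, and some of those patients may go on to withdraw.

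At stake is the accuracy of the one between-arm model estimate that SAP 3.9 plans for a safety outcome, in a population where motor worsening is a natural safety question.

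**Working it through.** **1. Can the reference be read as already including Week 4?** The printed primary contrast puts +1 in position 3 and −1 in position 6 of the treatment-by-visit term, with three visits for SYN120 followed by three for placebo. With four visits per arm the positions are SYN120 0, 4, 8, 16 and then placebo 0, 4, 8, 16. Position 3 becomes SYN120 Week 8 and position 6 becomes placebo Week 4. The four-level model has 1 shared baseline mean + 3 × 2 post-baseline means = 7 estimable means. Adding the printed contrast row raises the rank from 7 to 8, so the contrast is not estimable. The code works as printed only without Week 4 rows; with them, the contrasts must be rewritten.

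**2. The plan's own figures.** None is given for UPDRS. The only power figure is for the CDR endpoint, and it reproduces: 40 × 0.85 = 34 per arm, noncentrality 0.69 × √(34/2) = 2.845, two-sided 5% t-test power 0.8005. It does not bear on this point.

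**3. Size of the bias.** Every input here is an assumption.
- True effect: a sustained SYN120 worsening of 0.50 SD from Week 4.
- Withdrawal between Weeks 4 and 8 with probability 1/(1 + exp(−(m + 1.5z))), where z = (Y₄ − Y₀)/√(2(1 − ρ)), ρ is the Baseline–Week 4 correlation, and m is set to reach the stated rate.
- Correlation: compound symmetry (CS) at 0.5 to 0.85, or autoregressive (AR) at 0.95 per week.
- An Early Termination (ET) score, where present, is placed at Week 8.
- 200,000 simulated patients per arm; shared-baseline model fitted by sequential regression.

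| Withdrawal SYN120 / placebo | ET UPDRS | Three visits | Four visits |
|---|---|---|---|
| 15% / 5–9%, same rule in both arms | none | 0.473–0.487 | 0.498–0.504 |
| 30% / 13–20%, same rule | none | 0.460–0.475 | 0.500–0.502 |
| Both rows above | all | 0.476–0.490 | 0.494–0.501 |
| 15% / 7.5% and 30% / 15% | none | 0.459–0.478 | 0.500–0.509 |
| 15% / 0 | none | 0.452–0.454 | 0.500–0.506 |
| 30% / 0 | none | 0.403–0.410 | 0.499–0.502 |
| 15% or 30% / 0 | all | CS 0.445–0.470; AR 0.496–0.501 | 0.495–0.501 |
| 15% / 15% | none | 0.494 | 0.494–0.495 |
| 15% / 15%, unrelated to Week 4 | none | 0.501 | 0.501 |
| 15% / 30% | none | 0.540–0.544 | 0.497 |

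Where SYN120 loses more but placebo also loses some, with no ET data, attenuation runs from (0.50 − 0.487)/0.50 = 2.6% to (0.50 − 0.459)/0.50 = 8.2%. With SYN120-only loss it reaches (0.50 − 0.403)/0.50 = 19.4%. With more placebo loss the estimate is overstated by up to (0.544 − 0.50)/0.50 = 8.8%.

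**4. A harsher stress case.** Here there are 40 per arm, a true worsening of 0.30 SD, and visit correlation 0.7 or 0.8. Exactly the worst 5%, 10% or 15% of SYN120 Week 4 changers leave, placebo loses 2.5–5% at random, and there are no ET exams (600 trials per scenario). Three visits give 0.269, 0.259 and 0.221 at 0.7, and 0.276, 0.257 and 0.232 at 0.8. Four visits give 0.294–0.310. Attenuation is from (0.30 − 0.276)/0.30 = 8% to (0.30 − 0.221)/0.30 = 26%. A repeat with 400,000 per arm gave 0.226–0.230 at the 15% level and 0.297–0.301 throughout with four visits.

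**The case against.** The strongest reply is that the cross-reference was never meant literally. SAP 3.8.3 borrows the same model: "Non-key secondary efficacy endpoints and exploratory efficacy endpoints will all be analyzed using the mITT sample and the primary efficacy analysis". ADAS-cog is among those endpoints and is taken only at Baseline and Week 16 or Early Termination, so three levels cannot apply to it. In the SAS code, visit is a class variable; if Week 4 rows are in the dataset, the MODEL and REPEATED statements accept them. This stands in part. It shows that the reference has to be adapted by endpoint, so omission is the literal reading rather than a declared choice. It does not supply the UPDRS rule, and the printed contrasts fail with four visits.

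A reader might also infer that Week 4 scores are thrown away and that motor harm is understated. The documents do not support either. Week 4 is tabulated by arm. Patients who stop drug without withdrawing consent stay on schedule, so their Week 8 and Week 16 scores are still sought. Withdrawers are asked for an Early Termination visit with full UPDRS, and a score obtained between Weeks 4 and 8 enters the model at Week 8. These provisions shrink the bias, although under compound symmetry some remains even with every such score obtained. The direction depends on which arm loses more patients.

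The effect is also small beside sampling error. With one worst-changer rule across both arms, at 40 per arm and a true effect of 0.30 SD, the two models differed by 0.01–0.03 SD against a standard error of about 0.12–0.18 SD. Even the stress case, at 0.07–0.08 SD, is around half a standard error.

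Finally, this is not the only between-arm safety evidence. Protocol 10.5.1 plans Fisher's exact tests and negative binomial regression for adverse events, and SAP 3.10.2 a log-rank test of time to discontinuation.

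**Conclusion.** The point holds in a limited form. Followed as written, SAP 3.9.6 leaves a scheduled full-dose UPDRS assessment out of the between-arm model and loses the missing-at-random protection that the plan relies on. Bias in the Week 16 difference then needs three things together: withdrawal between Weeks 4 and 8 that depends on Week 4 scores, a difference between arms in that withdrawal, and incomplete capture at Early Termination (full capture reduces the bias and removes it only under some correlation patterns).

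Under the assumed inputs, attenuation is about 3–8% in moderate scenarios and about 20–26% at the extreme. It is about nil with equal or unrelated withdrawal, and the estimate is overstated if placebo loses more. The four-visit model returned 0.494–0.509 against a true 0.50 in every scenario of step 3. Severity is minor to moderate, because the estimate is supportive and Week 4 is still reported descriptively.

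**What to change.** In SAP 3.9.6:
- State that the UPDRS model has four visit levels (Baseline, Weeks 4, 8 and 16), treatment-by-visit terms at all three post-baseline visits, and a 4 × 4 unstructured within-person covariance.
- Rewrite the ESTIMATE coefficients for four visits. Keep Week 16 as the reported contrast and also report Weeks 4 and 8.
- Map Early Termination scores to the next visit on the UPDRS schedule. A score taken before Week 4 then goes to Week 4, a slot the three-visit model lacks.

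The cost is a short SAP addition and a few lines of code, with no new data. The covariance matrix grows from 6 to 10 parameters, four more to estimate from about 80 patients. That is the only real downside.
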